Title: Treatment of Full-Thickness Wounds: NPWT Combined with Type-I Collagen Based Advanced Skin Substitute Versus NPWT Alone

NCT No: NCT06873867

Date: November 09, 2025

INTRODUCTION

Full-thickness wounds, which extend through the dermis into the underlying subcutaneous tissue or deeper structures, remain a formidable challenge in reconstructive and wound care practice. These wounds may arise from trauma, surgical dehiscence, pressure injuries, or chronic ulceration, and are often complicated by infection, vascular insufficiency, and comorbidities such as diabetes and peripheral vascular disease. They affect millions of patients worldwide and impose substantial economic burden on healthcare systems [1, 2]. They are a growing concern in healthcare due to their prolonged healing time, high recurrence, and associated morbidity [3, 4]. These wounds often demonstrate delayed healing and increased risk of complications including infection, chronic inflammation, and impaired tissue regeneration [5, 6]. Without optimal management, these wounds fail to heal through the conventional stages of wound repair, functional impairment, increased risk of limb loss, poor cosmetic results and high healthcare costs. The complex pathophysiology of wound healing involves intricate interactions between cellular components, growth factors, extracellular matrix proteins, and vascular elements, necessitating comprehensive therapeutic approaches to optimize clinical outcomes [7].

Negative Pressure Wound Therapy (NPWT) has emerged as an effective modality to accelerate wound healing by removing excess exudate, enhancing perfusion, promoting granulation tissue formation and maintains an optimal wound environment, and thus is a cornerstone in treatment of complex wounds [8, 9, 10]. By applying controlled sub-atmospheric pressure, NPWT reduces interstitial edema, increases local blood flow, removes exudate, and stimulates granulation tissue formation. The application of controlled negative pressure creates a conducive environment for cellular proliferation and angiogenesis, facilitating the wound healing cascade [11, 12]. Despite its advantages, NPWT alone may not suffice for extensive tissue regeneration and achieve rapid epithelialization, especially in large or complex wounds where the extracellular matrix (ECM) and vascular supply has been significantly compromised [13].

The integration of biological skin substitutes in wound healing has emerged as a promising adjunctive therapy to enhance wound healing outcomes [14, 15]. High Purity Type-I Collagen (HPTC) skin substitutes, such as *Helicoll*[®], provide a bioactive scaffold that mimics native ECM, facilitating cellular migration, angiogenesis, keratinocyte proliferation and growth factor delivery. *Helicoll*[®] is an acellular dermal replacement product made of high purity (>97%) Type-I Collagen that provides a framework promoting blood vessel regeneration and biologic cell migration [16]. It is derived from bovine sources but processed to remove

antigenic components. *Helicoll*[®] undergoes a patented treatment process for purification, making it least immunogenic and highly biocompatible [17].

These bioengineered constructs offer several advantages including biocompatibility, biodegradability, and offer optimal bio-integration with host tissue while promoting natural healing processes [18, 19]. Recent RCTs have established its efficacy in chronic wound healing, including diabetic foot ulcers and venous leg ulcers [16, 20, 21]. Narayan et al. demonstrated that HPTC achieved significantly greater wound closure compared to dehydrated human amnion/chorion membrane (dHACM) in diabetic foot ulcers [16]. Similarly, an RCT in venous leg ulcers showed faster healing and better granulation quality with HPTC than dHACM [20]. Another dual-country RCT involving 55 patients reported consistent superiority of HPTC across different patient populations and healthcare settings [22]. These studies have shown superior healing rates, reduced healing time, and improved tissue quality compared to standard care approaches.

While these studies establish the role of HPTC in chronic ulcer management, the potential synergistic effect of combining HPTC with NPWT in full-thickness wounds has not been extensively studied. The rationale for combining NPWT with high-purity type-I collagen-based skin substitutes lies in their complementary mechanisms of action. Theoretically, NPWT could optimize the wound bed and vascular environment (mechanical environment), while HPTC provides the structural and biochemical support (biological framework) for accelerated tissue regeneration. This combination may result in faster and more complete healing than NPWT alone, addressing both the macroscopic and microscopic aspects of wound healing, potentially leading to superior clinical outcomes [12, 13, 20, 21, 23].

The present study aims to compare the clinical outcomes of NPWT combined with HPTC skin substitute versus NPWT alone in patients with full-thickness wounds, using a randomized controlled design, to provide robust evidence for clinical decision-making in advanced wound care. Our hypothesis is that the combination therapy will result in significantly greater wound area reduction, faster closure, improved scar quality, and better patient-reported pain outcomes, without increasing adverse events.

MATERIALS AND METHODS

This was a prospective, randomized, open-label, parallel-group clinical trial conducted at the Department of Plastic, Reconstructive, and Aesthetic Surgery, Adichunchanagiri Institute of Medical Sciences (AIMS), Karnataka, India. The study compared the efficacy of Negative Pressure Wound Therapy (NPWT) combined with High Purity Type-I Collagen (HPTC) skin substitute versus NPWT alone in the management of full-thickness wounds. Patient recruitment occurred between March 2025, and July 2025. The anticipated follow-up continued until August 2025, with each participant observed for a total of seven weeks (six weeks of intervention plus one-week follow-up). The trial was registered prospectively with **ClinicalTrials.gov (ID: NCT06873867)** and approved by the Institutional Ethics Committee (**Approval No: AIMS/IEC/013/2025**). The study adhered to the principles of the Declaration of Helsinki and Good Clinical Practice guidelines. All participants provided written informed consent prior to enrollment after comprehensive explanation of study procedures, risks, and benefits. Patient confidentiality was maintained throughout the study period.

Patients aged 18-80 years with full-thickness wounds (wound depth extending through dermis into subcutaneous tissue), including traumatic, post-surgical dehiscence, burns ulcers, pressure ulcers, DFUs, or VLUs, wound size $>20 \text{ cm}^2$ and $<75 \text{ cm}^2$, with adequate vascular supply to the wound site, ability to comply with treatment protocol and follow-up visits, and provided written informed consent were eligible.

Exclusion criteria included active infection or osteomyelitis requiring systemic antibiotics, active malignancy at wound site, immunosuppression, uncontrolled diabetes ($\text{HbA1c} > 9\%$), on systemic corticosteroids, patients on anticoagulation therapy with $\text{INR} > 3.0$ used advanced wound care products within the last 30 days, autoimmune or connective tissue disorders or allergy to bovine collagen.

Sample Size - Sample size calculation was based on the primary outcome of wound area reduction. Assuming a mean difference of 30% in wound area reduction between groups, with a standard deviation of 20%, power of 80%, and alpha of 0.05, a minimum of 47 patients per group was required. Accounting for 10% dropout rate, at 52 patients per group, with a total of 104 patients were recruited. This calculation was informed by effect sizes reported in previous HPTC RCTs in diabetic foot, venous leg and pressure ulcers, which demonstrated mean differences of 10–15% in wound healing outcomes. [6,7].

Randomization and Blinding - Participants were randomized 1:1 into two treatment groups using a computer-generated randomization sequence with block sizes of 4, 6, and 8. Patients were assigned to either: - Group A: NPWT + HPTC or Group B: NPWT alone.

Randomization was stratified by wound etiology. Allocation concealment was maintained using sequentially numbered, opaque, sealed envelopes prepared by a research assistant not involved in patient care or outcome assessment. Due to the nature of the intervention, complete blinding was not feasible; however, outcome assessors, pathologists, and data analysts were blinded to treatment allocation.

Intervention Protocol

Group A (NPWT + HPTC) - The wound was first debrided to remove necrotic tissue and ensure a viable wound bed. A sheet of High Purity Type-I Collagen skin substitute (Helicoll[®]) was applied to completely cover the wound surface. This was followed by a non-adherent porous dressing layer. NPWT was then applied using polyurethane foam at ~125 mmHg intermittent pressure (10 minutes on, 2 minutes off) for 5–7 days. The dressing was changed as per SOC thereafter, with repeat application of HPTC and NPWT as needed.

Group B (NPWT alone) - Following debridement, a non-adherent porous dressing was applied directly over the wound. NPWT was then initiated with the same parameters (polyurethane foam, ~125 mmHg, intermittent mode) and followed by SOC dressing. NPWT was reapplied if required.

All patients received standardized wound care including sharp debridement as needed to remove non-viable tissue, infection control with topical antimicrobials when indicated, pressure redistribution and offloading as appropriate, nutritional assessment and optimization, glycemic control for diabetic patients, compression therapy for venous ulcers and pressure offloading for wounds when appropriate. Patient education on wound care was given.

Outcome Measures

The primary outcome of the study was percentage wound area reduction from week 1 through week 6 plus 1 week follow up, measured via digital photography. Measurements were performed by trained personnel blinded to treatment allocation.

Secondary outcomes included time to complete wound closure (in days) within 7 weeks, proportion of patients achieving complete closure by week 7, histological vascularity infiltration, between baseline (Day 0) and Day 5 biopsies, mean number of applications of the skin substitute required, incidence of adverse events (infection, allergic reaction, bleeding,

maceration), pain score change using a 0–10 Visual Analog Scale (VAS) from baseline to week 6, and scar quality assessed at week 7 using the Manchester Scar Scale (MSS).

Complete wound closure is defined as 100% epithelialization. Histopathological assessment included taking punch biopsies (2 mm) from the wound edge at baseline and day 5 post-intervention under local anesthesia (2% lidocaine without epinephrine). Fixation in 10% neutral buffered formalin for 24 hours, processing through graded alcohol and paraffin embedding, and serial sectioning at 4 μ m thickness was done. Samples were processed using standard histological techniques and stained with hematoxylin and eosin (H&E), Masson's trichrome, CD31 immunohistochemistry, and α -SMA immunohistochemistry. Assessment parameters included vascular infiltration (0-3 scale), neo-epithelialization (0-3 scale), fibroblast activity (0-3 scale), capillary density (vessels per mm²), inflammatory response (0-3 scale) and collagen deposition (0-3 scale) (Table 1).

Quality of Life Assessment using EQ-5D-5L (EuroQol 5-Dimension 5-Level) [25] questionnaire, a standardized and widely used instrument for assessing health-related quality of life (HRQoL). Developed by the EuroQol Group [25], it provides a simple, generic measure applicable to a wide range of diseases and health conditions. The tool evaluates five key dimensions of health - mobility, self-care, usual activities, pain/discomfort and anxiety/depression. Each dimension is rated on five levels of severity - no problems, slight problems, moderate problems, severe problems and extreme problems or inability. These combinations describe a respondent's health state, which can be converted into a single summary index score (ranging from less than 0, indicating health states worse than death, to 1.0, representing full health) using country-specific value sets derived from general population preferences. In addition, the EQ-5D-5L [25] includes a Visual Analogue Scale (EQ-VAS) [25], a 0-100 scale on which patients rate their overall health (0 = worst imaginable health, 100 = best imaginable health). The EQ-5D-5L questionnaire was used in its validated Kannada Version 1.1 format, obtained directly from the EuroQol Group under non-commercial registration (ID: 78665). The tool was administered in interviewer-assisted digital format to ensure accurate comprehension by all participants.

Scar quality was assessed using Vancouver Scar Scale evaluating vascularity, pigmentation, pliability and height/thickness with total score ranging from 0 to 13 (lesser the score better the scar) (Table 2).

Table 1: Histological parameters evaluated in the ulcer bed at baseline and on day five of application

Parameter	Measurement tool	Criteria	Score
Vascular infiltration	Assessed by counting new blood vessels (0–3 scale)	Minimal vascular ingrowth (<5 vessels/HPF)	0
		Mild infiltration (5–10 vessels/HPF)	1
		Moderate infiltration (11–20 vessels/HPF)	2
		Abundant infiltration (>20 vessels/HPF)	3
Neo-epithelialization	Measured as epithelial migration distance from wound edge (0–3 scale)	No epithelial migration	0
		Minimal migration (<25% wound coverage)	1
		Moderate migration (25–75% coverage)	2
		Extensive migration (>75% coverage)	3
Fibroblast activity	Quantified by counting α -SMA positive fibroblasts per HPF and assessment of fibroblast morphology (0–3 scale)	Sparse, inactive fibroblasts	0
		Moderate cellularity, minimal matrix production	1
		High cellularity, active-matrix synthesis	2
		Very high activity with extensive matrix deposition	3
Capillary density	Evaluated using CD31 staining, counted as vessels per mm^2 of tissue		
Inflammatory response	Graded semi-quantitatively (0–3 scale)	Minimal inflammatory infiltrate	0
		Mild chronic inflammation	1
		Moderate mixed inflammation	2
		Severe acute inflammation	3
Collagen deposition	Assessed using Masson's trichrome staining (0–3 scale)	Minimal collagen matrix	0
		Loose, immature collagen	1
		Moderate organized collagen	2
		Dense, mature collagen architecture	3

Table 2: Vancouver Scar Scale

Parameter	Score
Vascularity	0–3
Normal	0
Pink	1
Red	2
Purple	3
Pigmentation	0–2
Normal (matches surrounding skin)	0
Hypopigmentation	1
Hyperpigmentation	2
Pliability	0–5
Normal	0
Supple (flexible with minimal resistance)	1
Yielding (gives way to pressure)	2
Firm (resists movement)	3
Banding / rope-like tissue (may blanch on extension)	4
Contracture (permanent shortening producing deformity)	5
Height / Thickness	0–3
Flat / normal	0
< 2 mm	1
2–5 mm	2
> 5 mm	3

Parameter	Score
Total Scar Score (Higher scores indicate greater scar severity)	0-13

Data Collection and Measurement

Wound photographs were obtained using standardized digital photography with measurement grids. Standardized wound assessments were performed including digital photography, wound measurements using validated techniques, and clinical evaluations. Wound area was calculated by tracing the wound margin onto a sterile transparent film and photographing with a scale reference. Histological evaluation was performed on wound biopsies with stains as mentioned in Table 1. Pain assessments (Visual Analogue Scale) and quality of life score were completed at baseline, every week thereafter for 7 weeks.

Statistical Analysis

All data were analyzed using SPSS version 26.0 (IBM Corporation, Armonk, NY). Continuous variables were expressed as mean \pm standard deviation and compared using independent t-tests or Mann–Whitney U tests where appropriate. Categorical variables were expressed as frequencies and percentages, compared using chi-square or Fisher’s exact test. Repeated measures ANOVA was employed for longitudinal outcome analysis. Time-to-event outcomes were analyzed using Kaplan-Meier survival analysis with log-rank tests.

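### The hypothesis of no increase in adverse events has no analysis that could support it: only chi-square or Fisher difference tests are listed, with no confidence interval or margin

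*Combined protocol and SAP*

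**What the plan says.** The last paragraph of the Introduction gives a single hypothesis. It lists several expected benefits of the combination and ends with "better patient-reported pain outcomes, without increasing adverse events".

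Outcome Measures makes safety a secondary outcome: "incidence of adverse events (infection, allergic reaction, bleeding", with maceration completing the list. It does not say whether incidence means patients with at least one event, each event type separately, or both.

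Statistical Analysis does not mention adverse events by name. Its general rule for such data is "Categorical variables were expressed as frequencies and percentages, compared using chi-square or" Fisher's exact test. The other listed methods are for continuous, longitudinal and time-to-event outcomes.

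The Sample Size paragraph concerns efficacy only: "Sample size calculation was based on the primary outcome of wound area reduction". It ends with 52 patients per group.

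Nowhere does the document give an expected adverse-event rate, a largest acceptable excess, a confidence interval for the difference, or a rule for concluding that events did not increase.

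**The concern.** The safety clause claims that something is absent, whereas chi-square and Fisher tests are built to find a difference. When they fail to find one, the data may be compatible with no increase and also with a large increase. The p-value does not say which. The smaller the trial or the rarer the event, the more easily p exceeds 0.05, so any error from leaning on the p-value favours the new treatment.

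At stake is the safety conclusion of a trial whose stated aim is to inform clinical decisions. The primary efficacy analysis is not affected.

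**Working it through.** **Inputs from the document.** 1:1 allocation; 52 per group recruited, 47 per group before the dropout allowance; alpha 0.05 (sidedness not stated, two-sided assumed); chi-square or Fisher for categorical data.

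**Inputs that must be assumed.** The control-arm event rate. A range of 5% to 30% is shown, each doubled in the combination arm.

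**The plan's own figure.** The Sample Size paragraph begins "Assuming a mean difference of 30% in wound area reduction between groups" and continues "with a standard deviation of 20%, power of 80%, and alpha of 0.05, a minimum of 47 patients per group was required". The usual formula gives

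n per group = 2 × (1.96 + 0.842)² × 20² / 30² = 2 × 7.85 × 400 / 900 = 6.98, that is 7.

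So 47 is not reproduced from these inputs. The step from 47 to 52 is 47 × 1.10 = 51.7. The mismatch is a separate matter. The safety point uses only the actual group size, and no adverse-event rate enters the calculation.

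**Power to detect a doubling, 52 per arm.** For every pair of counts (i, j), take the product of the binomial probabilities Bin(i; 52, p) × Bin(j; 52, 2p). Sum over the pairs with j > i at which the two-sided test is significant at 0.05.

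| Control vs combination (assumed) | Fisher | Uncorrected chi-square |
|---|---|---|
| 5% vs 10% | 7% | 15% |
| 10% vs 20% | 21% | 29% |
| 15% vs 30% | 37% | 46% |
| 20% vs 40% | 52% | 62% |
| 25% vs 50% | 70% | 77% |
| 30% vs 60% | 85% | 90% |

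Power crosses 50% at a control rate between 19% and 19.5% for Fisher, and between 16% and 16.5% for chi-square. With 47 per arm, the first three rows become 6%, 18% and 32% (Fisher) and 17%, 29% and 42% (chi-square).

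**What a non-significant result can hide.** Suppose 12/52 patients (23.1%) have an event on the combination and 5/52 (9.6%) on NPWT alone.

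- Fisher p = 0.11. For uncorrected chi-square, z = 0.1346 / √(0.1635 × 0.8365 × 2/52) = 1.86, so p = 0.063. Neither test is significant.
- The Wilson 95% limits are 13.7% to 36.1% and 4.2% to 20.6%.
- Newcombe lower limit: 13.5 − √[(23.1 − 13.7)² + (20.6 − 9.6)²] = −1.0 points.
- Newcombe upper limit: 13.5 + √[(36.1 − 23.1)² + (9.6 − 4.2)²] = +27.6 points (limits computed from unrounded values).

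The data would be compatible with an excess of more than 25 points, yet neither p-value falls below 0.05.

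**Identical counts.** With 5/52 in each arm, p = 1 and the Newcombe interval is ±√[(20.6 − 9.6)² + (9.6 − 4.2)²] = ±12.3 points. Even this result excludes only increases larger than 12.3 points.

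**The case against.** Two stronger readings are tempting, and the document supports neither.

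A reader might infer that the sponsor will declare safety shown once p exceeds 0.05. No such rule is written. Statistical Analysis gives only a generic rule for categorical variables, and its application to adverse events follows from incidence being categorical. The same rule calls for frequencies and percentages, so the event rates in each arm would be visible.

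A reader might also infer that a doubling would usually be missed. That depends on the unstated control rate. It holds up to about 15%. From 20% upward, either test at 52 per arm detects a doubling more often than not. The endpoint may pool four event types in wounds that the Introduction describes as often complicated by infection, so a pooled rate of 20% or more cannot be ruled out. Event by event, the rates can be no higher than the pooled rate, so the low end of the range still matters. Chi-square, which the plan also permits, has more power than Fisher in every row of the table.

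It is also fair to say that the safety clause closes a sentence mainly about benefit, that adverse events are one of several secondary outcomes, and that low power for them is common in a trial of this size.

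These objections limit how the point may be stated, but they do not remove it. The clause is part of the stated hypothesis, and no listed method could support it. That is true even where power is high, because failing to reject equality does not bound the size of an increase.

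**Conclusion.** The point stands in a limited form. As written, the plan has no analysis that can support the no-increase clause at any event rate: it lists difference tests only, gives no interval or margin, and is sized on another outcome.

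The numerical size is conditional. With 52 per arm, two-sided 0.05 and an assumed control rate of 5% to 15%, a doubling would be detected 7% to 37% of the time by Fisher and 15% to 46% by uncorrected chi-square. From a control rate of about 20% the chance exceeds one half with both tests. The document gives no rate from which to choose within this range. How the sponsor would in fact interpret p > 0.05 is not stated, and the conclusion does not rest on it.

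This should be corrected before a safety conclusion is reported.

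**What to change.** In Statistical Analysis, add that the between-arm risk difference in adverse events will be reported with a 95% confidence interval (Newcombe or Miettinen-Nurminen). Do this for patients with at least one adverse event and for each of the four listed events. Restate the safety part of the hypothesis as estimation. Limit the safety conclusion to the increase that the upper confidence limit excludes, and do not base it on p > 0.05. With 5/52 in each arm, for example, the report would say that increases above 12.3 points are excluded.

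A no-increase statement would need a justified margin. Recruitment ran from March to July 2025, follow-up was expected to end in August 2025, and the document is dated 9 November 2025. Any margin set now must therefore be disclosed as not prospective. Estimation alone avoids that difficulty.

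The cost is some rewording and a few intervals from counts already collected, with no new patients or data. The downside is a weaker safety statement.

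### The stated inputs (difference 30, SD 20, 80% power, alpha 0.05) give 7 to 9 patients per group, not 47, and the document does not show which input is misstated

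*Combined protocol and SAP*

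**What the plan says.** The Sample Size paragraph in Materials and Methods identifies the basis of the calculation: "Sample size calculation was based on the primary outcome of wound area reduction". It then gives the inputs, "Assuming a mean difference of 30% in wound area reduction between groups, with a standard deviation of 20"%, with power 80% and alpha 0.05, and the result: "a minimum of 47 patients per group was required". That figure is raised to 52 per group (104 in total) for 10% dropout. The paragraph closes by saying that the calculation drew on earlier trials of the collagen product, "which demonstrated mean differences of 10–15% in wound healing outcomes".

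Under Outcome Measures, "The primary outcome of the study was percentage wound area reduction". Under Statistical Analysis, continuous variables are to be "compared using independent t-tests or Mann–Whitney U tests where appropriate", and repeated measures ANOVA is named for longitudinal outcomes. Allocation is 1:1.

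The document does not state the sidedness of alpha, the formula or software used for the sample size, whether the 30% is absolute or relative, or an expected control-arm mean.

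**The concern.** A difference of 1.5 standard deviations (30/20) is very large, and a two-group comparison of means needs only a handful of patients per arm to detect it. A requirement of 47 per group belongs to a difference of a little under 0.6 SD. The inputs and the result therefore cannot both be right if the percentages are percentage points.

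The paragraph also sits uneasily with its own source. The assumed 30% is two to three times the 10–15% said to have informed it.

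This is the only justification for N on the primary outcome. If it cannot be reproduced, a reader cannot tell what effect the trial was designed to detect, or with what assumed variability. The candidate corrections describe materially different trials.

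**Working it through.** **Inputs.** From the Sample Size paragraph: difference 30, SD 20, power 0.80, alpha 0.05, stated n = 47 per group before dropout. From the randomization paragraph: 1:1 allocation. Two-sided testing is assumed because sidedness is not stated.

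**Attempt to reproduce 47, reading the figures as percentage points.**

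- Normal approximation: n = 2 × (1.96 + 0.8416)² × (20/30)² = 6.98, so 7 per group.
- Exact (noncentral) t-test: n = 8.06, so 9 per group. Power is 0.797 at n = 8 and 0.848 at n = 9.

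47/9 = 5.2 and 47/7 = 6.7, so the stated n is about five to seven times what the inputs give. Dropout does not explain it, because 47 is the figure before inflation. (47 × 1.1 = 51.7, which rounds up to the stated 52.)

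**Variants that might close the gap.**

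| Variant (difference 30, SD 20) | n per group |
|---|---|
| One-sided alpha 0.05, 80% power, normal | 5.50, so 6 |
| One-sided alpha 0.05, 80% power, t-test | 6.30, so 7 |
| Mann–Whitney at worst-case efficiency 0.864 | 8.06/0.864 = 9.33, so 10 |
| t-test, 90% power | 10.40, so 11 |
| t-test, 95% power | 12.60, so 13 |
| t-test, 99% power | 17.36, so 18 |

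Repeated measures ANOVA does not help. If 30 points is the difference averaged over visits, averaging equally correlated measurements cannot increase the variance, so the between-group comparison needs at most the 7 found above (normal approximation).

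**Working back from n = 47 (two-sided, 80% power).**

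- (a) Keep SD 20. The detectable difference is (1.96 + 0.8416) × 20 × √(2/47) = 11.56 points (normal), or 11.68 points (t-test).
- (b) Keep 30 points. The SD would have to be 51.9 (normal) or 51.4 (t-test).
- (c) Keep SD 20 points and read 30% as a relative difference. This needs a control mean, and none is given. With assumed control means (t-test):

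| Assumed control mean reduction | Difference in points (0.30 × mean) | n per group |
|---|---|---|
| 33.3% | 10.0 | 64 |
| 39% | 11.7 | 47 |
| 50% | 15.0 | 29 |

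- (d) A 30-point difference between two proportions, with continuity correction, gives 44.9 to 48.8 per group for assumed control rates of 20–50%. The text gives a mean difference and an SD, so it does not describe this calculation, but this may be what was run.

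**What the alternatives imply at 47 per group.** With SD 20, t-test power is above 99.9% for 30 points, 94.9% for 15, 80.1% for 11.7 and 66.9% for 10. The expected 95% confidence interval half-width is t(0.975, 92 df) × SD × √(2/47), which is 8.2 points at SD 20 and 20.9 points at SD 51.

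**The case against.** The strongest reply is that the error is harmless. Under the stated inputs the trial is larger than it needs to be. Recruitment is also over ("Patient recruitment occurred between March 2025, and July 2025"), so no participant, test or estimate changes with the correction. The achieved confidence interval will come from the observed SD, whichever planning figure was wrong. This is right as far as it goes: the finding is not one of inadequate power, and the contrast in half-widths describes planning uncertainty, not the eventual result. But the reassurance holds only if the stated inputs are the true ones, and that is what the paragraph fails to establish. If the intended difference was 10 points with SD 20, power at 47 is 67%.

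A second reply is that the 10–15% effects need not match the 30%. The Introduction describes the earlier diabetic-foot and venous-ulcer trials as comparisons with another skin substitute, whereas the control here has none, so a larger effect could be expected. The references cited in the Sample Size paragraph are also not the ones the Introduction gives for those trials, and the earlier effects are for wound healing outcomes in general. This stands. The 10–15% is a sign of inconsistency and does not show that 30% is the wrong number, even though 11.7 falls inside that range.

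A third reply is that no test is expressly assigned to the primary outcome, so the t-test is an assumption. That is also true, but no test named under Statistical Analysis brings the requirement near 47.

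**Conclusion.** The concern holds. With a 30-point difference, SD 20, two-sided alpha 0.05 and 80% power, the requirement is 7 (normal) or 9 (t-test) per group, against 47 stated. No standard variant of a two-group comparison of means using those inputs closes the gap.

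The conclusion rests on reading both percentages as percentage points. The primary outcome's own scale and the mean-and-SD wording support that reading. The relative reading reaches 47 only with a control mean of about 39% that the document does not supply.

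The document does not identify which element is wrong. The difference, the SD, the scale or the type of calculation could each account for 47, and the working does not choose among them. The paragraph is wrong or incomplete as written and must be corrected, but no additional patients are needed.

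**What to change.** The sponsor should retrieve the original calculation, correct whichever element was misstated (difference, SD, scale or type of endpoint), and restate the paragraph so that effect, SD, sidedness, test, power and N agree. If the calculation was for a comparison of means, a suitable form is:

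> Assuming a difference of [x] percentage points [or a relative difference of 30% from a control mean of y%] and a standard deviation of [z] percentage points, a [two]-sided [t-test] at alpha 0.05 with 80% power requires 47 patients per group.

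If it was for a difference in proportions, the paragraph should say so, give the control rate, and explain why that outcome was used to size a trial whose primary outcome is continuous.

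The text should also state that it was corrected after recruitment ended, and explain how the 10–15% effects were used. If SD 20 is confirmed, it would help to add that 47 evaluable patients per group give 80% power for about 11.7 points, 67% for 10 and 95% for 15, and that these figures are conditional on SD 20 and were not a pre-specified target.

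If the calculation cannot be recovered, the document should say so and list the readings that fit 47. The result should then be interpreted from its confidence interval, without reference to a planned effect that cannot be verified.

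The cost is wording plus the search for the original calculation. N, conduct and analysis are unchanged. The sponsor may have to acknowledge that an input was misreported or is lost.
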